3. OBJECTIVE

3.1. Primary Objective

To develop an algorithm for the diagnosis of viral and bacterial pathogens in pediatric patients with pneumonia.

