3.2. Secondary Objectives

- To identify the etiologies of pneumonia in children in Indonesia, which are currently unavailable.
- To document outcomes in pediatric patients with pneumonia in Indonesia.
- To evaluate the performance of each rapid point of care test (to detect influenza and viral syncytial viruses, legionella urinary antigen, biomarkers of bacterial infections (CRP and PCT), and standard of care procedures (Chest X-ray, O₂ saturation, CBC, blood Gas Analyses (if available) compared to the gold standard molecular assays in differentiating virus and bacterial infections.
- To analyze the performance of combined tests in differentiating virus and bacterial infections.
- To provide information regarding updated strains of circulating respiratory viruses and pathogens in children.

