4.4. Population and Sample Size

This is a preliminary study to characterize the pathogens present in this cohort. The number of participants' that will be enrolled is based on the number of pneumonia cases in 5 years old children or less. This study plan to enroll with total of 275 participants.

With 275 participants, the 95% confidence interval for the prevalence of each pathogen will be no greater than $\pm 7\%$. The study is not powered to test the diagnostic accuracy of the algorithm. The algorithm developed from this study will be evaluated in a larger study, powered to estimate sensitivity and specificity. As a result, no formal power calculations have been provided.

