6.2. Analysis

An interim analysis will be conducted every 3-6 months to discuss the operation and challenges of the screening and enrollment process, the collection of data and specimens, and to analyze the results of bacterial culture, biomarkers, rapid diagnostic tests, molecular and serogical assays.

It is expected that the gold standard measurements will fall into three categories: confirmed viral (33%), confirmed bacterial (20%), and mixed/unconfirmed (47%). For purposes of algorithm development and assessment, we will combine the latter two groups (confirmed bacterial and mixed/unconfirmed) into a single group. The justification for the grouping is that clinically, a patient who receives a mixed/unconfirmed diagnosis will likely be treated in the same manner as a patient with a confirmed bacterial diagnosis.

As this is a preliminary study, we will fit the data using a variety of different approaches for combining diagnostic tests, including classification and regression trees, random forests, and multivariate logistic regression. For models with binary outputs, we will calculate the sensitivity and specificity (defined using confirmed bacterial as "cases" and confirmed viral as "controls"). For models with continuous outputs, we will calculate the receiver operating characteristic (ROC) curve. The relative performance of the models will primarily be evaluated based on sensitivity and specificity. 10-fold cross-validation or similar methods will be used to account for potential over optimism from fitting multiple models.

While clinical relevance is of primary importance, we may also consider algorithms that perform three-category classifications (with the categories as originally defined), as such results may be of etiologic interest. Furthermore, for all analyses, we may consider calculating the positive predictive value (PPV) and negative predictive value (NPV); while sensitivity and specificity are of primary importance, PPV and NPV may provide further useful descriptive information.

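### Section 6.2 does not require model and cutoff choice to be repeated inside the cross-validation folds; if the winner's own result is reported, accuracy is overstated by about 0.5 to 2.6 points on average (fixed cutoff, assumed signal)

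*Combined protocol and SAP*

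**What the plan says.** Section 6.2 (Analysis) will fit "a variety of different approaches for combining diagnostic tests, including classification and regression trees, random forests, and multivariate logistic regression". The word introducing the three families leaves the list open. On comparison it says: "The relative performance of the models will primarily be evaluated based on sensitivity and specificity". On models that produce a score it says only: "For models with continuous outputs, we will calculate the receiver operating characteristic (ROC) curve". One sentence deals with optimism: "10-fold cross-validation or similar methods will be used to account for potential over optimism from fitting multiple models".

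The section does not mention an inner loop, a hold-out set, a rule for combining sensitivity and specificity into one criterion, or a rule for setting a cutoff. It does not say which model's figures will be reported as the accuracy of the algorithm.

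The primary objective (section 3.1) is "To develop an algorithm for the diagnosis of viral and bacterial pathogens in pediatric patients with pneumonia", and a secondary objective (section 3.2) is "To analyze the performance of combined tests in differentiating virus and bacterial infections". Section 4.4 states: "The study is not powered to test the diagnostic accuracy of the algorithm". It leaves evaluation of the algorithm to a later, larger study.

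**The concern.** Cross-validating one model removes the advantage that model gains from being tested on its own training data. It does not remove the advantage gained by comparing several cross-validated results and keeping the highest. Each result carries sampling error, and the highest tends to be one whose error was favourable. This is the kind of optimism the sentence in section 6.2 says it will account for, yet the simplest method that complies leaves it in place.

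The cutoff adds a second layer. Logistic regression gives a probability, and a random forest can give a continuous score. Neither can be compared on sensitivity and specificity until a cutoff is set. If that cutoff is read off the ROC curve of the same held-out predictions, the resulting figures are optimistic for that reason too.

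At stake is the accuracy this study reports, not necessarily which algorithm it selects. The reported figure answers a secondary objective and is a natural input when the later study is sized, although the protocol does not say it will be used that way. The later study will evaluate the algorithm afresh, but it does not correct what is published from this one.

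**Working it through.** **Inputs from the protocol.** Section 4.4 gives 275 participants. Section 6.2 expects 33% viral, 20% bacterial and 47% mixed or unconfirmed:

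- viral: 0.33 × 275 = 90.75, about 91
- bacterial: 0.20 × 275 = 55
- mixed/unconfirmed: 0.47 × 275 = 129.25, about 129

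Models are developed on 55 + 129 = 184 versus 91. Sensitivity and specificity are assessed on 55 versus 91.

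**The plan's own figure.** The plan gives no number for optimism. Its one computed figure, the ±7% bound on a prevalence, is not in dispute: 1.96 × √(0.25/275) = 5.9 points, which is inside the bound.

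**Sampling error.** At an assumed sensitivity of 0.80 and specificity of 0.75, the standard error of (sensitivity + specificity)/2 is 0.5 × √(0.16/55 + 0.1875/91) = 3.5 points. The 95% half-width is 1.96 × 3.5 = 6.9 points.

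**Approximation by hand.** For k equally good models whose results correlate at ρ, the expected excess of the best is SE × √(1 − ρ) × E[max of k standard normals]. The last term is 0.846 for k = 3 and 1.163 for k = 5. With ρ from 0.8 to 0.5:

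- k = 3: 3.52 × 0.447 × 0.846 = 1.3, up to 3.52 × 0.707 × 0.846 = 2.1 points
- k = 5: 3.52 × 0.447 × 1.163 = 1.8, up to 3.52 × 0.707 × 1.163 = 2.9 points

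**Main simulation.** None of the following assumptions is in the protocol.

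- Set A: 15 independent normal predictors, 5 informative, with mixed/unconfirmed children halfway between the other two groups.
- Set B: 8 predictors with correlation 0.3, 3 informative, with each mixed/unconfirmed child viral-like or bacterial-like at random.
- Candidates: logistic regression, a depth-3 tree and a 100-tree forest (three); plus ridge logistic and a depth-2 tree (five); plus naive Bayes and 15-nearest-neighbour (seven).
- Winner: highest cross-validated (sensitivity + specificity)/2.
- Fixed cutoff: training prevalence. Chosen cutoff: best on the pooled held-out scores, with trees kept at the fixed cutoff.
- Truth: the winner refitted on all 275 and applied to 3,000 bacterial and 3,000 viral new subjects.
- 340 replicates per setting; simulation standard error 0.2 to 0.3 points.

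Mean overstatement in points, at AUC 0.70 / 0.80 / 0.90:

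| Candidates | Set A, fixed | Set B, fixed | Set A, chosen | Set B, chosen |
|---|---|---|---|---|
| One logistic model | 0.0 / -0.3 / -0.3 | 0.0 / 0.3 / -0.3 | – | – |
| Best of 3 | 1.8 / 0.9 / 0.5 | 1.8 / 1.5 / 0.5 | 5.0 / 3.8 / 3.0 | 5.0 / 4.2 / 3.0 |
| Best of 5 | 2.6 / 1.4 / 0.7 | 2.3 / 2.0 / 0.8 | 5.4 / 4.0 / 3.2 | 5.3 / 4.3 / 3.1 |
| Best of 7 | 3.4 / 2.3 / 1.4 | 3.2 / 2.6 / 1.4 | 6.0 / 4.6 / 3.7 | 5.8 / 4.6 / 3.3 |

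A single pre-specified model shows essentially no bias, so the excess comes from selection. Nested 10-fold cross-validation differed from the truth by -0.7 to +0.3 points across all 36 settings. One example (set A, AUC 0.80, best of five, fixed cutoff): reported 0.691, true 0.676, nested 0.671.

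This is an average effect. With three to five candidates the reported figure exceeded the truth in 55–70% of replicates at a fixed cutoff, and in 81–92% when the cutoff was also chosen.

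**Second simulation, different design.** This used 12 predictors (5 informative), L1 logistic and a shallow tree as the two extra candidates, and 120 data sets per setting. For moderate to strong signal at a fixed cutoff the excess was 0.7–2.1 points (three candidates) and 1.4–2.7 (five). For weak signal it was 2.4–2.9 and 3.3–4.0. With the cutoff chosen on the held-out predictions it was 2.5–6.6 over all settings. Candidates without selection averaged -0.1 to +0.5.

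Nesting was checked at one moderate signal with three candidates. At a fixed cutoff, ordinary cross-validation was +1.1 (SE 0.45) and nested -0.1 (SE 0.5). With the cutoff chosen, the figures were +3.7 (SE 0.4) and 0.0 (SE 0.5).

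**The case against.** The strongest reply is that the plan already names this bias. Its stated purpose is optimism across models, and its wording allows nested cross-validation or a bootstrap, so what is missing is implementation detail. The harm also needs a step the plan does not describe: picking the maximum and publishing that model's own figure. The simulated selection rule, cutoff and signal are mine. Choosing partly on simplicity would usually reduce the bias, and the upper 2.6 needs two candidates the plan does not name together with the weakest signal.

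The bias is also small against the noise. At the example's true value of 0.676, taken for both sensitivity and specificity, the half-width is 1.96 × 0.5 × √(0.219/55 + 0.219/91) = 7.8 points, against a bias of 0.691 − 0.676 = 1.5. Finally, section 6.2 calls the study preliminary, section 10.7 calls it a pilot, and section 4.4 leaves accuracy to a larger study.

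Much of this stands. The size is conditional, the range for the three named families is 0.5 to 1.8, and the choice of algorithm need not suffer. But permission to nest is not a commitment to it, and selection cannot be repeated inside folds until a criterion and a cutoff rule exist. Lack of power concerns imprecision. Selection bias is systematic, and a confidence interval around the winner's own result does not correct it.

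**Conclusion.** The concern holds. It is worth changing and does not block the study. As written, section 6.2 can be followed to the letter while leaving in the optimism it sets out to remove. If the winner's ordinary cross-validated result is presented as its accuracy, expect (sensitivity + specificity)/2 to be overstated on average by about 0.5 to 2.6 points with three to five candidates at a fixed cutoff. If the cutoff is picked on the same held-out results, expect 3.0 to 5.4 points.

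These sizes rest on assumed predictors, candidates and signal, because the protocol gives no expected accuracy. They shrink as signal strengthens and grow when it is weak (up to about 4 points at a fixed cutoff in the second simulation). The finding about the text is firm; confidence in the exact size is moderate.

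**What to change.** Replace the cross-validation sentence in section 6.2 with text such as:

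> The candidate models, one selection criterion (for example the highest (sensitivity + specificity)/2 for confirmed bacterial versus confirmed viral) and a cutoff rule will be fixed before analysis. Variable selection, tuning, model choice and cutoff choice will be repeated within each training set, using nested 10-fold cross-validation stratified by reference category, or a bootstrap of the whole selection process. The outer-loop or bootstrap-corrected sensitivity and specificity, with confidence intervals, will be reported as the accuracy of the algorithm-selection procedure; ordinary cross-validated results for every candidate will be shown as descriptive.

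The cost is three sentences, agreement on the list and rules before analysis, and more computing: 10 outer folds × (10 inner fits + 1 refit) = 110 fits per candidate instead of 10. No extra participants, specimens or visits are needed.

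With three to five candidates the reported figure will fall by about 1.0 to 2.9 points at a fixed cutoff, or 3.3 to 5.8 if the cutoff would otherwise have been chosen on held-out results. The nested figure may be slightly pessimistic (up to 0.7 point here). It remains imprecise: each inner fold holds about 5 bacterial children, and nesting does not narrow the 6.9-point half-width.

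### Section 6.2 permits a single unstratified 10-fold run, so when models perform similarly the random partition can decide which algorithm is chosen; stratified, repeated cross-validation on shared folds removes this at almost no cost

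*Combined protocol and SAP*

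**What the plan says.** Section 4.4 sets the size: "This study plan to enroll with total of 275 participants". Section 6.2 expects the reference standard to classify 33% of children as confirmed viral, 20% as confirmed bacterial and 47% as mixed or unconfirmed. For development, "we will combine the latter two groups (confirmed bacterial and mixed/unconfirmed) into a single group", so all 275 children are used. Sensitivity and specificity are narrower: cases are the confirmed bacterial children and controls are the confirmed viral children.

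The candidate approaches are left open, "including classification and regression trees, random forests, and multivariate logistic regression". On choosing between them: "The relative performance of the models will primarily be evaluated based on sensitivity and specificity". On internal validation: "10-fold cross-validation or similar methods will be used to account for potential over optimism from fitting multiple models".

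The section does not state the number of repeats, whether folds are stratified, whether all models share the same folds, the seed, or how sensitivity and specificity are combined into a ranking. Section 4.4 adds: "The study is not powered to test the diagnostic accuracy of the algorithm". It defers evaluation of the algorithm to a larger study.

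**The concern.** Developing the algorithm is the primary objective, and cross-validation is the only internal check on the choice between models. A cross-validated estimate depends on the data and also on how the children happened to be divided into folds. With few evaluable children, the second source can be large enough to reorder models of similar performance.

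Two analysts could then follow section 6.2 to the letter, on the same data, and carry different algorithms into the larger study. The published sensitivity and specificity would also include a random component that nobody reports. Unlike sampling error, this component can be removed without enrolling another child.

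**Working it through.** **The plan's own figure.** No figure is given for the stability of cross-validation. The only stated precision is a 95% half-width of at most 7 points for the prevalence of each pathogen. The worst case is 1.96 × √(0.5 × 0.5 / 275) = 5.9 points, so that statement holds. It concerns all 275 children and does not carry over to sensitivity or specificity.

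**Evaluable children** (sections 4.4 and 6.2).
- Confirmed bacterial: 275 × 0.20 = 55. Confirmed viral: 275 × 0.33 = 90.75, about 91. Mixed or unconfirmed: 275 × 0.47 = 129.25, about 129.
- Per fold, on average: 27.5 children, of whom 5.5 are bacterial and 9.1 viral.
- One reclassified child moves sensitivity by 1/55 = 1.8 points and specificity by 1/91 = 1.1 points.

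**Unstratified folds.** In random equal splits of 275 children with exactly 55 bacterial, the smallest bacterial count in any fold was 0, 1 or 2 in 1.5% + 11.7% + 35.1% = about 48% of splits (50,000 draws).

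**Noise from the partition alone.** This needs marker effects that the documents do not give, so it was simulated under assumed moderate effects with the 33/20/47 shares. The SD between re-splits of the same data, in percentage points, was:

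| Simulation | Logistic | Tree | Random forest |
|---|---|---|---|
| A: 25 datasets, 40 unstratified splits each (sensitivity/specificity) | 2.4/2.2 with 18 inputs; 1.6/1.6 with 4 inputs | 6.0/5.2 | no value |
| B: 6 datasets at each of two signal strengths, 15 stratified splits each, trained on 275 (sensitivity) | 2.1 and 1.7 | 4.4 and 5.1 | 3.9 and 3.1 |
| C: separate simulation of 275 children | about 2 | about 5 | no value |

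**Change of winner.** In B, models were ranked by J = sensitivity + specificity − 1.
- A: the winner differed from the most frequent winner in 16% of splits. This is a different quantity from disagreement between two splits.
- B, trained on all 275: two splits disagreed in 32% and 38% of pairs on average at the two signal strengths (0% to 65% by dataset). Trained only on the 146 confirmed children: 24% and 31%.
- C: 23% of pairs on average (0% to 52% by dataset), and no disagreement between two 20-repeat averages.

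**Effect of repeating.** Let s be the split-to-split SD of the difference in J between two models, d the split-averaged gap and K the number of repeats. Taking splits as independent given the data, p = Φ(d√K / s), and two analysts disagree with probability 2p(1 − p). B gave s of 0.046 to 0.051 for logistic regression against random forest when trained on 275; take 0.05.
- d = 0.05, K = 1: p = Φ(1) = 0.841, disagreement 27%. K = 20: under 0.1%.
- d = 0.02, K = 1: p = Φ(0.4) = 0.655, disagreement 45%. K = 20: 7%. K = 50: 0.5%.
- d = 0: 50% at any K.

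**Sampling error for comparison, at a true 80%.**
- Sensitivity: SE = √(0.8 × 0.2 / 55) = 5.4 points; half-width 1.96 × 5.4 = about ±10.6.
- Specificity: SE = √(0.8 × 0.2 / 91) = 4.2 points; half-width about ±8.2.
- If the two sources are independent, the logistic split SDs in A raise the total SD by between √(5.4² + 1.6²)/5.4 − 1 = 4% and √(4.2² + 2.2²)/4.2 − 1 = 13%. For the tree, split noise (6.0/5.2) is about as large as the sampling SE (5.4/4.2).

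**The case against.** The strongest reply is that the plan never commits to the weak procedure. A reader might infer that section 6.2 prescribes one unstratified split; it does not. Neither term appears, and the allowance for similar methods already covers repeated or stratified cross-validation and the bootstrap. That stands: the point is what the sentence permits. But permission is not a requirement, and a one-off run would comply fully.

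A reader might also infer that only 55 + 91 = 146 children are split. The documents do not support this. All 275 enter development, and 55 and 91 are only the denominators of sensitivity and specificity.

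Nor does a sparse fold make the estimate invalid. The plan does not say that sensitivity is computed within folds. If held-out predictions are pooled, the denominator stays at 55, and a fold with 2 bacterial children still leaves 53 for training.

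The ranking is not always unstable. In B the same model won all 15 splits in 5 of 24 combinations of dataset, signal strength and training set. Switching occurs mainly when models are close, and choosing either then costs little; no loss of true accuracy from a switch has been shown. For logistic models, sampling error is clearly the larger uncertainty. The study is also described as preliminary, with evaluation to follow. All of this limits the importance of the point. It does not remove it, because the algorithm selected here is the one the larger study is meant to evaluate.

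**Conclusion.** The point holds as a low-cost improvement to the primary analysis, not as an error in the plan. The text permits a single unstratified run. With such a run, the partition alone would move sensitivity and specificity with an SD of about 2 points for logistic models and about 5 to 6 for a tree (4.4 at the lowest, with stratified folds). When models are close, identical data can yield different chosen algorithms, in roughly 23% to 38% of split pairs on average and 0% to 65% by dataset.

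The counts of 55 and 91 follow from the plan's expected shares. The simulated figures rest on assumed predictors, effects and model settings and, in B, on six datasets per scenario; they are indicative only. The switching rates in B also assume ranking on J, because the plan gives no rule for combining sensitivity and specificity.

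The documents do not support a conclusion that the chosen algorithm would be wrong or its accuracy biased for this reason.

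**What to change.** In section 6.2, replace the cross-validation sentence with a statement that 10-fold cross-validation will be:
- stratified on the three reference categories (confirmed viral, confirmed bacterial, mixed/unconfirmed);
- run on the same folds for every candidate model;
- repeated, for example 50 or more times, with models ranked on the average over repeats and the between-repeat SD reported beside each estimate.

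The exact number of repeats is not critical. With s = 0.05, 20 repeats settle a gap of 0.05 in J and 50 largely settle a gap of 0.02. Exact ties will not be resolved, and the report should say so where the averaged difference is small against its between-repeat SD. Confidence intervals for sensitivity and specificity are still needed, because repeating does nothing for sampling error. The cost is a short addition to the text and computing time, with no extra children, visits or specimens.

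### Mixed and unconfirmed children form one class (about 129 of 275), and the measures used to compare models would not show a model that classes mixed infections as viral

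*Combined protocol and SAP*

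**What the plan says.** Section 6.2 (Analysis) expects the reference measurements to give three categories: confirmed viral 33%, confirmed bacterial 20% and mixed/unconfirmed 47%. For developing and assessing the algorithm, "we will combine the latter two groups (confirmed bacterial and mixed/unconfirmed) into a single group". The reason given is that a mixed or unconfirmed child would probably be managed like a confirmed bacterial one.

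Sensitivity and specificity are then defined on a narrower set: confirmed bacterial children are the cases and confirmed viral children the controls. Models are to be compared mainly on these two measures, with 10-fold cross-validation or a similar method. PPV and NPV may be added as description.

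The section closes with an optional extension: "we may also consider algorithms that perform three-category classifications (with the categories as originally defined), as such results may be of etiologic interest".

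Etiology is also a secondary objective in its own right (section 3.2): "To identify the etiologies of pneumonia in children in Indonesia". Section 4.4 plans a prevalence with a confidence interval for each pathogen. Section 6.3 (Operational Definitions) does not define confirmed, mixed or unconfirmed.

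**The concern.** Two things do not fit together.

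First, the only argument for pooling concerns treatment. It supports the two-group algorithm. It says nothing about an analysis run for etiologic interest, where a child with both a virus and a bacterium differs from a child with no confirmed cause. Keeping them together makes the largest of the three expected classes one with no clear etiologic meaning, and a three-category classifier would be trained to predict it.

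Second, the training rule puts mixed children with the bacterial cases, but the assessment measures leave them out. A model could classify confirmed bacterial and confirmed viral children well, call most mixed infections viral, and still rank first. That is the error the plan's own grouping argument is meant to avoid, and it bears on the primary objective of developing the algorithm.

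**Working it through.** **Inputs.** N = 275 (section 4.4). Expected shares 33%, 20% and 47% (section 6.2). The split of the 47% into mixed and unconfirmed is not in the documents, so 25%, 50% and 75% mixed are assumed as a range. A flagged proportion of 80% is also assumed.

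**1. The plan's own precision figure.** Section 4.4 states at most ±7 points for the prevalence of each pathogen. In the worst case, p = 0.5: 1.96 × √(0.25/275) = 0.059, or 5.9 points. The statement holds. It concerns single pathogens and does not depend on the three categories.

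**2. Expected class sizes.** The shares sum to 100%.
- Confirmed viral: 0.33 × 275 = 90.75, about 91.
- Confirmed bacterial: 0.20 × 275 = 55.
- Mixed/unconfirmed: 0.47 × 275 = 129.25, about 129.

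**3. Who enters the comparison measures.** Sensitivity uses 55 children and specificity about 91. Together that is 146 of 275 (53%). The other 129 (47%) enter neither.

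**4. What the measures can see.** Sensitivity is the number flagged among the 55 divided by 55. Specificity is the number not flagged among the 91 divided by 91. Neither formula contains a mixed child. As an illustration, take two models that each flag 44 of the 55 (80%) and have the same specificity. Suppose half the pool, about 65 children, is mixed. If one model flags all 65 and the other flags none, their sensitivity and specificity are identical.

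**5. Precision if the groups are reported separately.** Half-width = 1.96 × √(0.8 × 0.2/n). The mixed group has f × 129.25 children.

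| Group | n | Half-width (points) |
|---|---|---|
| Confirmed bacterial | 55 | 10.6 |
| Mixed, f = 25% | about 32 | 13.9 |
| Mixed, f = 50% | about 65 | 9.7 |
| Mixed, f = 75% | about 97 | 8.0 |

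The unconfirmed group is the mirror image: about 97, 65 or 32 children.

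**The case against.** The strongest reply has four parts.

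- **The three-category algorithm is optional and is not the plan's whole etiologic analysis.** This stands. Section 4.4 plans per-pathogen prevalence, and Tables 1 and 2 list an 18-virus and an 11-bacterium PCR panel, with blood PCR, culture and serology besides. The objection to the class applies only if that classifier is run.

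- **Training already places mixed children with bacterial ones, so a model is penalised during fitting for calling them viral.** This is true of fitting each model. It does not reach the choice between models, which rests mainly on sensitivity and specificity. Section 6.2 says the grouping also serves assessment, but the two measures it then defines do not use it. PPV and NPV are optional, and their denominators are not stated.

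- **Restricting sensitivity and specificity to confirmed children is defensible, because the rest have no clear reference label.** This stands, and nothing here asks for those definitions to change. It is a better argument for unconfirmed children than for mixed ones, if mixed means that both a virus and a bacterium were established.

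- **The study is preliminary.** Section 4.4 says it is not powered for diagnostic accuracy and defers that to a larger study. This lowers the weight of the point. It does not remove it, because the algorithm carried into the larger study is developed here.

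**Conclusion.** The point holds as a cheap improvement. About 129 of 275 children (47%) sit in a class whose pooling is justified only by treatment. The stated sensitivity and specificity would not reveal a model that classes mixed infections as viral. The sizes rest on the plan's expected shares, and on reading mixed as viral plus bacterial, which the documents do not say.

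Three stronger readings are tempting and are not supported.

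- A reader might infer that the share of children with any bacterial pathogen can be known only to lie between 20% and 67% (20% + 47%). That range limits the category labels, not the study data: a share can be computed from per-child pathogen results. It also uses expected shares and undefined terms. What remains is that the plan names no such summary, and per-pathogen prevalences do not add up to one when a child carries several pathogens.
- A reader might infer that the study could not show how the algorithm handles mixed infections. Predictions and pathogen results will exist for each child, so the tabulation is possible; it is just not pre-specified.
- A reader might infer that splitting the pool makes sensitivity more precise. Reported separately, the confirmed bacterial group stays at 55 children and 10.6 points. The gain is in seeing the mixed group.

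**What to change.** Leave the two-group training rule and the stated sensitivity and specificity as they are. Add to sections 6.2 and 6.3:

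1. Definitions of confirmed, mixed (viral plus bacterial) and unconfirmed, applied to the per-child results already planned, with mixed and unconfirmed recorded as separate categories.
2. A table of the cross-validated proportion flagged as not viral, given separately for confirmed bacterial, mixed and unconfirmed children with 95% confidence intervals, and a statement that it will be considered when models are compared.
3. Four categories instead of three if the etiologic classifier is run.

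The cost is a few lines of definition, one more category in the code and one more table. No new specimens, tests or participants are needed. The downside is smaller cells: if only a quarter of the pool is mixed, that group has about 32 children and a half-width near 14 points, so its result would be descriptive.
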